5.1.1.8. Duration of Grade 4 Neutropenia

Grade 4 neutropenia is defined as the lab value of ANC \geq Grade 4 event CTCAE toxicity grade criteria (i.e. ANC value is $< 0.5 \times 10^9/L$). For the treatment period, the total number of Grade 4 neutropenia events is the number of cycles where at least one ANC value is $< 0.5 \times 10^9/L$. For example, if Cycle 2 has two ANC values that are both $< 0.5 \times 10^9/L$, this only counts as one event. If a patient did not have any ANC \geq Grade 4 events, the value of 0 will be assigned to that patient. Unscheduled data and the actual assessment date (rather than visit date) will be included in the derivation.

Within each cycle, the duration (days) of each reported Grade 4 neutropenia event is defined as the number of days from the date of first ANC value of $< 0.5 \times 10^9/L$ observed between start of cycle and end of cycle, to the date of first ANC value $\geq 0.5 \times 10^9/L$ that meets the following criteria: (1) occurs after the ANC value of $< 0.5 \times 10^9/L$ and (2) no other ANC values $< 0.5 \times 10^9/L$ occur between this day and end of cycle. The following censoring rules will be applied in the calculation:

- (i) For a cycle where the Grade 4 neutropenia event does not resolve by end of the cycle, the duration will be assigned as above except the end date will be the end of cycle.
- (ii) For a cycle where the patient dies, withdraws consent, or is lost to follow-up during the Grade 4 neutropenia event, the duration will be assigned as above except the end date will be the date of the last ANC assessment prior to the end of cycle.

For the treatment period, the overall duration (days) of Grade 4 neutropenia events is the median value among the duration (days) of Grade 4 neutropenia events from all cycles. The following data handling conventions will apply:

- For those patients where all event duration values are derived from cycles with censored data, the median value for that patient will be the median censored value. It will be a considered a censored value;
- For those patients where a subset of event duration values are derived from cycles with censored data, the median value for that patient will be estimated using the KM method. It will be considered as an observed value (i.e. no censored value);
- For those patients where the median event duration cannot be derived (e.g. ≤ 2 values), the longest event duration amongst all the cycles will be used regardless of censoring, but the corresponding censoring flag will be carried over for analysis.

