**Table 9-1 Schedule of Assessments**

Cycle Day	Screening	Enroll	Cycle 1 and Every Odd Cycle a (21 days)					Cycle 2 and Every Even Cycle a (21 days)					Last Cycle	Post-Treatment Visit b	Survival Follow-up c		
	-14	-3 to 1	1	2	3	8	10	15	1	2	3	8	10	15	22		
Informed Consent d	X																
Demographics	X																
Medical History e	X																
Eligibility Eval.	X	X															
Performance Status	X		X					X								X	
Physical Exam	X		X					X								X	
Height, Weight & Vital Signs f	X		X					X								X	
Clinical Chemistry	X		X g			X		X	X g			X		X		X	
Hematology	X		X h		X	X	X	X	X h		X	X	X	X	X	X	X
Urinalysis	X		X g						X g							X	
ECG	X		X i		X j											X	
Pregnancy test k	X		X					X									
Randomization l		X															
Tumor Assessment m	X m2												X		X m1,m2	X m1	
Tumor Testing n		X															
PK o			X		X												
G1T28 or Placebo p			X	X	X				X	X	X						
Carboplatin			X						X								
Etoposide			X	X	X				X	X	X						
FACT-L and FACT-An q			X				X		X				X		X		
Immunologic Marker r			X												X	X	
AEs s	X									X							
Con. Medications	X									X							
Survival Follow-up c																	X

AE = adverse event; ECG = electrocardiogram; FACT-AN = Functional Assessment of Cancer Therapy – Anemia quality of life instrument; FACT-L = Functional Assessment of Cancer Therapy – Lung quality of life instrument; PRO = patient reported outcome; Eval. = evaluation; PK = pharmacokinetics

- a G1T28 or placebo + E/P therapy will continue until disease progression, unacceptable toxicity, or discontinuation by the patient or investigator (eg, after completing 6 cycles). The tumor should be assessed after every even cycle. Assessments should be performed within 7 days of starting the subsequent cycle.
- b Patients will return to the study center for a Post-Treatment Visit at 30 days (+ 3 days) after the last dose of study drug.

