5. PRIMARY AND SECONDARY ENDPOINTS

The following general definitions will be applied to all endpoints derivation unless otherwise specified.

Term	Definition
Grade 4 neutropenia	ANC lab value that meets the common terminology criteria for adverse events (CTCAE) criteria for \geq Grade 4 toxicity
Grade 3/4 neutropenia	ANC lab value that meets the CTCAE criteria for \geq Grade 3 toxicity
Cycle baseline	The last non-missing value within the window starting from 3 days prior to the date/time of study drug administration on Day 1 of Cycle 1 and 1 day prior to Day 1 of each subsequent cycle (i.e. Cycle 2, Cycle 3, etc); must be prior to the time of study drug administration
Cycle NADIR	The lowest value for a given hematologic parameter that occurs between start of cycle and end of cycle and is less than the cycle baseline.
Duration of cycle	Total number of days from start of cycle to end of cycle, that is, date of end of a cycle - date of start of cycle + 1.
End of cycle*	Day 1 of the subsequent cycle. For example, the end of cycle for Cycle 1 is Day 1 of Cycle 2. For the last cycle (where no subsequent cycle is given), the end of cycle will be defined as Day 36.
Start of cycle	Day 1 of each cycle starts with the administration of study drug(s) (etoposide, carboplatin or trilaciclib)
Start of study	Day 1 of Cycle 1
Study baseline	The last non-missing value prior to, or on the date of administration of study drug(s) (etoposide, carboplatin or trilaciclib); must be prior to the time of study drug administration
Change from baseline	Calculated as the post-baseline value minus the baseline value. If the baseline value is missing for a particular endpoint, change from baseline will be missing.
Treatment period	Total number of days from start of cycle for Cycle 1 and end of cycle for the last cycle

* For various hematologic parameter analyses, the last assessment prior to end of cycle will be utilized in the analyses. Situations where this applies will be indicated as such.

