[c] Hematology may be obtained up to 3 days prior to first dose of G1T28/placebo + EP therapy in Cycle 1, and 1 day prior to first dose for subsequent cycles.

[d] Patient-reported outcomes should be completed at Days 1 and 10 of each cycle and at the Post-Treatment Visit. If a cycle is delayed, the patient should still complete the PRO on the scheduled Day 1 of the next cycle, as well as the actual first dosing day of the next cycle of G1T28 or placebo + E/P therapy. Patient-reported outcomes may be obtained up to 24 hours prior to the first dose of each cycle of G1T28 or placebo + E/P therapy.

[e] 60 ± 7 days after the post-treatment visit only for hematologic parameters and immunologic biomarker. The data is collected only for patients in Part 2.

[f] If Day 1 is included in the windowing, the associated assessment must be post G1T28 infusion.

Note: The end date of a cycle (EOC) is defined as the date of Day 1 study drug administration of its next cycle. For the last cycle (where no subsequent cycle is given), the end of cycle will be defined as Day 36 relative to the first dose of the cycle. Hence, for the last cycle, the window for EOC is 19-36.

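### Unresolved neutropenia is censored at the end of the cycle (Day 36 in the last cycle) instead of at the last ANC, so unobserved days can count as time still neutropenic

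*SAP*

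**What the plan says.** SAP 5.1.1.8 measures a Grade 4 episode from the first ANC below 0.5 × 10⁹/L in a cycle to the first later ANC at or above that level with no further low value before the cycle ends. Two exceptions follow, introduced by "The following censoring rules will be applied in the calculation":

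- Rule (i): for an event that "does not resolve by end of the cycle, the duration will be assigned as above except the end date will be the end of cycle".
- Rule (ii): for a cycle "where the patient dies, withdraws consent, or is lost to follow-up during the Grade 4 neutropenia event", "the end date will be the date of the last ANC assessment prior to the end of cycle".

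SAP 5.1.1.9 has the same two rules for Grade 3/4 with a threshold of 1.0 × 10⁹/L.

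The end of a cycle is Day 1 of the next one. SAP Section 5 adds: "For the last cycle (where no subsequent cycle is given), the end of cycle will be defined as Day 36". A footnote there says that some hematology analyses use the last assessment before the end of cycle and that this will be indicated where it applies. Rule (ii) indicates it; rule (i) does not.

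The patient-level value is the median over event cycles. If every value is censored, it is the median censored value, kept as censored. If a median cannot be derived, for instance with two or fewer values, "the longest event duration amongst all the cycles will be used regardless of censoring", and the censoring flag is carried forward. SAP 6.2.7.1 analyses both durations by Kaplan-Meier, with a stratified p-value and a Cox hazard ratio with 80% CI.

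**The concern.** Kaplan-Meier and Cox methods read a censoring time as the last moment at which the patient was known to be event-free, here known to be still neutropenic. Rule (i) sets that time by the calendar, not by a measurement. A patient whose last count was low and who has no later count by Day 36 stays in every risk set up to Day 36 as if neutropenia had been confirmed throughout.

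Rule (ii) shows that the authors saw the difficulty, but it covers only three reasons for a missing count. A patient who stops treatment for progression, toxicity or investigator decision, misses the later blood counts and is still followed for survival meets none of the three. Protocol 10.8 says that such patients should be encouraged to complete the remaining assessments; it does not guarantee that the counts exist.

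Both durations are among the prospectively defined analyses in SAP Table 3 and are compared between arms of about 35 patients, so a few such values can move a hazard ratio.

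**Working it through.** **Inputs.** Last-cycle end, Day 36 (SAP Section 5). Hematology on Days 1, 3, 8, 10 and 15, with Day 22 in the last cycle (Protocol Table 9-1). "Post-Treatment Visit at 30 days (+ 3 days) after the last dose of study drug", which is Day 3 + 30 = 33 to Day 3 + 33 = 36 if the last dose is on Day 3. Start of a next cycle requires ANC ≥ 1.5 × 10⁹/L (Protocol 6.1.3). The plan gives no figure for these endpoints. Its only precision figures (±0.157 and ±0.344 SD with 35 per arm) reproduce but play no part here.

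**Step 1: where rule (i) acts.** A cycle followed by another normally ends with an ANC of at least 1.5, which is a qualifying recovery for both thresholds. Rule (i) therefore matters almost only in the last cycle.

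**Step 2: unobserved days.** With no ANC after the first low value, rule (i) gives 36 minus the day of that value. Censoring at the last ANC gives 0.

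| Day of lone low ANC | Rule (i) | Last ANC |
|---|---|---|
| 8 | 36 − 8 = 28, censored | 0, censored |
| 10 | 36 − 10 = 26, censored | 0, censored |
| 15 | 36 − 15 = 21, censored | 0, censored |
| 22 | 36 − 22 = 14, censored | 0, censored |
| 33 | 36 − 33 = 3, censored | 0, censored |

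**Step 3: patient-level value** (lone low ANC on Day 15 of the last cycle).

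| Earlier resolved 7-day events | Rule (i) | Last ANC |
|---|---|---|
| none | 21, censored | 0, censored |
| one | 21, censored (longest of 7 and 21) | 7, observed |
| two | 7, observed | 7, observed |
| five | 7, observed | 7, observed |

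With one earlier event, rule (i) replaces an observed recovery by a censored value. With three or more event cycles in all, these examples do not change.

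**Step 4: group level, assumed data.** Take patients with at least one event and durations of 2, 5, 7, 12 and 14 days with probabilities 0.10, 0.25, 0.35, 0.20 and 0.10. The mean is 0.2 + 1.25 + 2.45 + 2.4 + 1.4 = 7.7 days. Let a share f instead have a single Day 15 last-cycle value and no later count. Under rule (i) the mean restricted to 21 days is (1 − f) × 7.7 + f × 21; under last-ANC censoring it stays at 7.7. The share still unresolved just after day 7 under rule (i) is f + (1 − f) × 0.30.

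| f | Restricted mean, rule (i) | Unresolved after day 7 |
|---|---|---|
| 5% | 7.315 + 1.05 = 8.4 | 0.335 |
| 10% | 6.93 + 2.1 = 9.0 | 0.37 |
| 20% | 6.16 + 4.2 = 10.4 | 0.44 |

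The Kaplan-Meier median stays at 7 days in all three rows because the unresolved share is below one half. The curve's tail and the hazard ratio carry the effect.

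**Step 5: direction, assumed data.** Start from 13 placebo episodes of 2–12 days and 6 trilaciclib episodes of 2–7 days, chosen so that the Cox hazard ratio for resolution is about 1.25 (Efron ties). Then add patients censored at 21 days.

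| Added on placebo | Added on trilaciclib | Hazard ratio, about |
|---|---|---|
| 0 | 0 | 1.25 |
| 2 | 0 | 1.63 |
| 4 | 0 | 1.99 |
| 2 | 1 | 1.03 |
| 1 | 1 | 0.89 |

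If the added patients are censored at their last ANC (day 0), they enter no risk set and the ratio stays at 1.25. The sign of the shift depends on which arm the missing counts fall in.

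**The case against.** The best defence is that the exposed group is small. Day 22 and Post-Treatment counts are scheduled. Protocol 11.3.2 requires clinically significant values to be re-measured, Protocol 10.8 calls for abnormal drug-related results to be repeated until they resolve or are explained, and SAP 5.1.1.8 uses unscheduled counts by actual date. Day 36 is not arbitrary: it is the late edge of the Post-Treatment window and Day 22 plus the two-week maximum delay, and SAP 6.1.3 matches it ("Hence, for the last cycle, the window for EOC is 19-36"). When the later counts exist, the gap closes or shortens. All of this stands. It limits how often the rule misfires, but it does not justify censoring beyond the data when it does.

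A reader might infer two stronger things. The first is that weeks of neutropenia are counted as observed durations. They are not: the values are censored and the flag is carried to the patient level. The second is that the rule favours trilaciclib, because more last-cycle neutropenia is expected on placebo. The documents do not support this. They give neither the number of such patients nor their arm, and step 5 shows the ratio falling when missing counts are spread over both arms.

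Two other points deserve weight. Protocol 13.2.3 calls the study descriptive, without formal testing between arms, although SAP 6.2.7 attaches p-values at a two-sided 20% level. And censoring a lone low value at day 0 removes a patient with documented severe neutropenia from the duration comparison, which is a real cost.

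**Conclusion.** The point holds in a limited form. Rule (i) censors at a calendar date instead of the last measurement, in both duration endpoints and in contrast to rule (ii). For a patient still on study with a lone low last-cycle value on Day 8 to Day 22, 28 down to 14 unobserved days enter the risk sets. The value reaches the analysis mainly through patients with one or two event cycles.

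This rests on the ANC start criterion protecting earlier cycles, and on at least some patients lacking a count after a low last-cycle value. How many do is not stated. The group-level figures rest on assumed data and show sensitivity only. The size and direction of any distortion in this trial are unknown. This is a correction worth making before unblinding, not evidence that the comparison is biased towards either arm.

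**What to change.** In SAP 5.1.1.8 and 5.1.1.9, replace rule (i) by: if no qualifying recovery ANC is recorded by the end of the cycle, censor at the date of the last ANC assessment on or before the end of the cycle. Keep the end-of-cycle version as a sensitivity analysis. Report, by arm, the number of patients whose last ANC in the cycle was low with no later count, and the number censored at day 0.

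The cost is one sentence in each of two sections, one extra run and no new data. The drawback is that a patient with a lone low value then adds no duration information, which is why the counts by arm are needed. Component 5 of the MAHE endpoint (SAP Table 5) does not change, because any censored Grade 4 duration already counts as meeting it.

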### 6.1.3. Criteria for Subsequent Cycles and Study Duration

In all parts of the study, study drug administration will continue until disease progression per Response Evaluation Criteria in Solid Tumors (RECIST), Version 1.1, unacceptable toxicity, withdrawal of consent, or discontinuation by investigator (eg, after completing 6 cycles), whichever occurs first. Treatment cycles will occur consecutively without interruption, except when necessary to manage toxicities or for administrative reasons as described below.

In order to start Cycle 2 and subsequent cycles as scheduled, patients should meet all of the following criteria:

- ANC  $\geq 1.5 \times 10^9/L$
- Platelet count  $\geq 100 \times 10^9/L$

- Nonhematologic drug-related toxicities (except alopecia) must be  $\leq$  Grade 1 or have returned to baseline

A delay of up to 2 weeks is permitted to allow recovery from any toxicity in order to meet the continuation criteria for organ function. If patients meet the criteria for starting the subsequent cycle as described above, a delay of up to 1 week is permitted for administrative reasons (eg, holiday, vacation, etc.). If the subsequent cycle is delayed, the patient should still complete the clinical laboratory assessments and the FACT-L and FACT-An questionnaires on the scheduled Day 1, as well as on the actual first dosing day of the next cycle. A patient will be discontinued from the study if recovery from any toxicity, in order to meet the continuation criteria for organ function, and any delay for administrative reasons requires a total delay of  $> 2$  weeks (see Section 8.4.4.2.1 and Table 8-2).

After discontinuation of study drug, patients should be strongly encouraged to complete all scheduled assessments through the end of their current 21-day treatment cycle, including the patient-reported outcome (PRO) scales; CBC assessment on Day 22; the Post-Treatment Visit; and the Survival Follow-up Phase of the study.

The G1T28-02 study will be completed when the Survival Follow-up Phase has been completed, or upon sponsor termination of the study.

The total study duration is at least 29 months.

Part 1 is expected to be approximately 18 months, assuming 12 months of accrual, 2 weeks for screening, 4.5 months of treatment (assuming 6 cycles), and 1 month of safety follow-up.

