- For those patients where the median event duration cannot be derived (e.g. ≤ 2 values), the longest event duration amongst all the cycles will be used regardless of censoring, but the corresponding censoring flag will be carried over for analysis.

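### Overall neutropenia duration is a median over affected cycles but becomes the longest episode when there are two values, which inflates the score only for patients with exactly two affected cycles

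*SAP*

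**What the plan says.** For the treatment period, SAP 5.1.1.8 states that a patient's overall duration "is the median value among the duration (days) of Grade 4 neutropenia events from all cycles". Three conventions follow.

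- If all values are censored, "the median value for that patient will be the median censored value".
- If some are censored, "the median value for that patient will be estimated using the KM method", and the result counts as observed.
- For patients "where the median event duration cannot be derived (e.g. ≤ 2 values), the longest event duration amongst all the cycles will be used", and the censoring flag of that value is carried over.

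Section 5.1.1.9 has the same text for Grade 3/4 neutropenia, including "the longest event duration amongst all the cycles will be used regardless of censoring".

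For a patient without events, 5.1.1.8 says "the value of 0 will be assigned to that patient". That sentence follows the definition of the number of events and comes before duration is defined.

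SAP 6.2.7.1 analyses both durations by Kaplan-Meier, with a p-value stratified by ECOG status and a Cox hazard ratio. The significance level is two-sided 20%.

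**The concern.** The clause treats two values as having no median, which is wrong for uncensored data. A programmer who follows the text will use the median for most patients and the maximum for those with exactly two affected cycles. The score then means different things at different event counts, and a patient with more neutropenia can score lower than one with less.

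If the arms differ in how many patients have exactly two affected cycles, the comparison moves for a reason unrelated to how long episodes last. Time to first MAHE is not affected, because its neutropenia component uses the within-cycle duration.

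Two smaller gaps sit in the same paragraphs. The order of the three conventions is not given, and the SAP does not say outright that event-free patients enter the duration analysis with 0.

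**Working it through.** **Plan's own figures.** The SAP gives no sizing for this endpoint. Its only precision figures reproduce for n = 35: t(0.975, 34)/√35 = 0.3435 (stated 0.344), and the largest Wilson half-width is 0.1572 (stated 0.157). Nothing below depends on them.

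**Step 1: the score by number of affected cycles (uncensored).**

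| Durations (days) | SAP score | Ordinary median |
|---|---|---|
| 7 | 7 | 7 |
| 7, 14 | 14 | (7+14)/2 = 10.5 |
| 7, 7, 14 | 7 | 7 |

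One value is its own median, and three or more values already use the median. Only the two-value row differs.

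**Step 2: expected inflation at two.** Assume durations of 2, 5, 7, 12 and 14 days with probabilities 0.15, 0.20, 0.45, 0.10 and 0.10. The cumulative probabilities F are 0.15, 0.35, 0.80, 0.90 and 1.

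- Ordinary median of two: its expectation is the mean, 0.30 + 1.00 + 3.15 + 1.20 + 1.40 = 7.05.
- Longest of two: weights are the differences of F², so 2(0.0225) + 5(0.1000) + 7(0.5175) + 12(0.1700) + 14(0.1900) = 8.87.
- Three values: 6.83 under both rules.

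The inflation is 8.87/7.05 = 1.26. Exponential, normal and lognormal shapes (also assumed) give 8.99/6.00 = 1.50, 7.69/6.06 = 1.27 and 7.23/5.66 = 1.28.

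**Step 3: can censoring explain the clause?** The SAP's general definitions say "the end of cycle for Cycle 1 is Day 1 of Cycle 2". Protocol 6.1.3 says "In order to start Cycle 2 and subsequent cycles as scheduled, patients should meet all of the following criteria", and the list includes ANC at or above 1.5 × 10⁹/L. That is above both thresholds (0.5 and 1.0), so under the protocol only the last cycle can be censored. With one censored value, a Kaplan-Meier median (first time at or below one half) exists in every pattern for two to six events, so a protocol-compliant patient rarely needs the fallback. The overlap that remains is one observed plus one censored value. For 7 observed and 14 censored, the curve falls to 0.5 at day 7 and stays there. The second convention gives 7 (or no median, if strictly below one half is required); the third gives 14, censored.

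**Step 4: effect on the comparison.** All rates here are assumptions. Inputs: 35 per arm, 6 cycles, the Step 2 grid in both arms, independent durations within a patient, no censoring, zeros included, 4 of 35 per arm with ECOG 2, and a stratified log-rank test at two-sided 20%. There were 1,500 trials per scenario (Monte Carlo SE at most 1.3 points per chance). Protocol 4.1 cites neutropenia of 47% to 92% without grade or unit. Read as the share of placebo patients affected, it gives per-cycle risks of 1 − 0.53^(1/6) = 10.0% and 1 − 0.08^(1/6) = 34.4%.

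The share affected is 1 − (1−p)⁶ for independent cycles and where each event halves later risk. With beta variation between patients (a+b = 4) it is 1 − ∏(4(1−p)+i)/(4+i), i = 0 to 5. The nine scenarios inside the range are:

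| Dependence | Risk per cycle, placebo/trilaciclib | Placebo affected | Shift in chance favouring trilaciclib (SAP minus ordinary median) |
|---|---|---|---|
| Independent | 10/5% | 47% | +5 |
| Independent | 30/10% | 88% | +10 |
| Independent | 34/17% | 92% | +11 |
| Between-patient variation | 30/10% | 74% | +4 |
| Between-patient variation | 34/17% | 79% | +3 |
| Between-patient variation | 50/25% | 92% | −4 |
| Event halves later risk | 10/5% | 47% | +3 |
| Event halves later risk | 30/10% | 88% | +12 |
| Event halves later risk | 34/17% | 92% | +22 |

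The extremes are 69% − 47% = +22 and 46% − 50% = −4. At the +22 scenario, 37% of placebo and 14% of trilaciclib patients have exactly two affected cycles.

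**Step 5: sensitivity.** If trilaciclib also shortens episodes (assumed probabilities 0.30, 0.30, 0.30, 0.05, 0.05), the nine shifts are at most about 4 points either way. With equal rates in both arms, the SAP rule rejects in about 9% to 12% of trials in each direction, against 10% nominal.

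**The case against.** The clause may be meant only as a fallback for a Kaplan-Meier median that is not reached. That fits the words about a median that cannot be derived, but the sole example given is two or fewer values, with no mention of censoring, so the text does not limit it that way.

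The rule is pre-specified and blind to arm, and it does not raise the false-positive rate. This stands. The harm is to the meaning of the score and to sensitivity.

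The ordinary median is not monotone either: 7 and 14 score 10.5, while 7, 7 and 14 score 7. This also stands, but the ordinary median is the SAP's own definition and treats every count alike.

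The larger shifts depend on the drug changing only how often episodes occur. SAP Section 4 expects less marrow damage with trilaciclib, so unchanged episode length is not a neutral assumption. This stands and limits the size claimed.

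On event-free patients, zero is the more plausible reading. The sentence is in the duration section, the FAS governs efficacy (SAP 3.1.1), and 6.2.7.1 does not analyse the event count. What is missing is an explicit statement.

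These are two of 17 rows in SAP Table 3, in a study that the protocol calls descriptive.

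**Conclusion.** The point holds and should be fixed. For uncensored data the longest-episode clause departs from the SAP's own median at exactly two affected cycles and nowhere else, and it raises the expected score there by roughly 26% to 50% under the assumed duration distributions. Its effect on the chance of p<0.20 favouring trilaciclib is about −4 to +22 points in the nine scenarios, and a few points if the drug also shortens episodes. The actual size in this trial cannot be derived from the documents.

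A reader might infer three stronger things that the documents do not support.

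- **That the rule can reverse the comparison.** A reversal appears in simulation at 60% versus 30% per cycle with independent cycles. That implies 1 − 0.4⁶ = 99.6% of placebo patients affected, outside the range cited in Protocol 4.1.
- **That the rule inflates false positives.** Rejection under no effect stays near nominal.
- **That event-free patients are left out.** The text is not explicit, but zero is the likelier intention.

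The order of conventions and the zeros are therefore secondary clarifications. Two censored values, where the first and third conventions conflict, should not arise in a protocol-compliant patient.

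**What to change.** Before unblinding, amend SAP 5.1.1.8 and 5.1.1.9 as follows.

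1. Use the ordinary median, or the Kaplan-Meier median where some values are censored, at every event count including two. Keep the longest value with its censoring flag only where a Kaplan-Meier median is not reached. Delete the example of two or fewer values.
2. State that the Kaplan-Meier convention takes precedence over the fallback for one observed plus one censored value, and define the Kaplan-Meier median as the first time the curve is at or below one half.
3. State that event-free FAS patients enter with an observed duration of 0 and stay in the stratified test and Cox model. Show duration among affected patients descriptively only.

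If a score that cannot fall when an episode is added is wanted, use the longest episode or total days at every count instead.

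The cost is a few sentences and re-programming of two derived variables. No new data, endpoint or test is needed. Because the main summary then includes zeros, duration among affected patients needs its own display.
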